5. TRIAL DESIGN

The overall trial design, depicted in the flowchart below, is a parallel group, open label study randomising to RFW or FAW in permuted blocks in adults aged 60 years or over who are undergoing hemiarthroplasty following hip fracture. The trial has been designed with input from cross-specialty hospital consultants, patient representatives, a statistician and a clinical trials unit. This pilot study will recruit for a minimum of one year at each site, allowing for refinements to design, site selection and, if necessary, the data management strategy in preparation for a large multi-centre trial.

Participants will be expected to remain in the trial for approximately three months. They will not need to attend any research specific clinics or undergo any study specific clinical investigations. The primary endpoint is numbers recruited and observed event rate for definitive deep surgical site infection (SSI) within 90 days as defined by the Centre for Disease Control (CDC). All potential primary endpoints will be confirmed by a blinded endpoint committee. The secondary endpoints include serious adverse events including death, superficial SSI, IPH, length of hospital stay, patient reported outcome measures (EQ-5D-5L) and resource utilisation. Data for all assessments will be captured either from routine clinical care records or by telephone contact with participants or their GP practice at baseline, 30 (+/- 7) days and 90 (+/- 14) days. Patients will be flagged and mortality checks performed at each time point before the local study team makes contact for follow-up. Where a potential deep SSI is identified, a summary of the clinical care record, redacted for all personal identifiable information and any indication of randomisation arm, will be forwarded to the independent blinded endpoint committee.

CONFIDENTIAL Page 11 of 34

Endpoint Committee

The endpoint committee, which will remain blind to allocation, will comprise clinicians with expertise in the diagnosis and management of bone and joint infection. The committee will have a chair and two other members. If any endpoint committee member stands down during the course of the trial, they will be replaced by someone with similar background and qualifications.

Any post-randomisation re-admission, clinic attendance or return to theatre with signs and symptoms at the site of surgery (i.e. possible deep surgical site infections) will be considered a potential primary endpoint. A summary of the relevant medical record, redacted for personal identifiers and information relating to randomisation, will be forwarded to the blinded endpoint committee who will determine if an endpoint has been met. Determination of an endpoint will be by consensus following discussion or by a majority vote called by the chair if consensus cannot be reached.

Secondary endpoints, including SAEs and data for resource utilisation, will be determined directly by the local investigators.

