Follow-Up Time Points	Participants will be followed up at 30 days and 90 days following surgery.	
Primary Outcome Measure	Recruitment rate and data completion (pilot study) and definitive deep surgical site infection (SSI) within 90 days of surgery (main trial).	
Secondary Outcome Measures	come Measures Superficial SSI, documented IPH, length of hospital stay, patient reported	
	outcome measures for quality of life score (EQ-5D-5L), resource utilisation and serious adverse events (SAEs) including death.	

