7.6. Subsequent Assessments

The participant will be contacted for follow-up at the following time points after surgery:

- 1) 30 (+/- 7) days
- 2) 90 (+/- 14) days

Follow-up assessments will be undertaken by a member of the local study team through a) medical records and b) direct contact, usually by telephone, with the participant or their consultee. The participant will not be asked to attend any research specific clinic visits and they will not be visited at home by the study team. If it is not possible to make contact with the participant, the local study team will gather follow-up data from the patient's GP and from routinely collected surveillance data. At each time point, we will ask questions about the participant's wellbeing, surgical scar and any treatment or concerns around possible infection at the operative site. Where necessary, further clinical review will be requested.

The study will use the participant follow-up telephone questionnaire in Appendix A as a research tool when gathering patient reported outcome measures for quality of life (PROMS) and any relevant concerns they have. Instructions to the participant will be dictated from the EQ-5D-5L telephone questionnaire in Appendix B. If a patient lacks capacity, the EQ-5D-5L Proxy version 1 will be used (Appendix C).

Deep SSI will be defined by the following criteria:

- a. Infection arising within 90 days of the index surgery (where day 1 is the procedure date) AND
- b. Involves deep tissues related to the incision (e.g. fascial and muscle layers, joint space or periprosthetic region)

AND

- c. At least one of the following
 - i. Purulent drainage from the deep incision or periprosthetic drain.
 - ii. A deep incision that spontaneously dehisces, or is deliberately opened or aspirated or biopsied by a surgeon, physician or other designee and an organism is identified by a culture or non-culture based microbiologic testing method which is performed for purposes of clinical diagnosis or treatment (e.g., not Active Surveillance Culture/Testing) or culture or non-culture based microbiologic testing method is not performed
 - An abscess or other evidence of infection involving the deep incision or periprosthetic region that is detected on gross anatomical, histopathological exam or imaging test

Superficial SSI will be defined by the following criteria:

- a. Infection arising within 30 days of the index surgery (where day 1 is the procedure date) AND

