7.7. Definition of End of Study

The end of the study is defined as the date of the last follow-up telephone call to the last participant recruited. Any planned formal analyses of the data will take place after this time point.

8. WARMING METHOD and TEMPERATURE MONITORING

The participants recruited to this study will all undergo hemiarthroplasty. During their surgery the patient will be kept warm as part of their standard care. The primary method used will be either Forced Air Warming (FAW) or direct contact Resistive Fabric Warming (RFW) depending on the randomisation arm to which they have been allocated. Both FAW and RFW are established and licensed for use in the UK and are equally effective at preventing inadvertent perioperative hypothermia (Negishi et al.2003). The warming devices will be used in accordance with national guidelines as defined in NICE CG65. Where necessary for optimal clinical care, additional warming methods can be employed at the discretion of the supervising clinician. Standard clinical care would normally include actively warming intravenous fluids and blood products in all patients.

Temperature will be monitored throughout the surgical procedure at all recruiting sites. All thermometers will be calibrated according to the standard protocol at each site. Where possible, site will use the 'SpotOn zfd' temperature monitoring system provided by the company 3MTM (Patient Warming Solutions).

As part of standard clinical care the patient's temperature will be measured and documented before induction of anaesthesia and every 30 minutes until the end of surgery. For the binary analysis, IPH will be defined as a temperature of <36°C at the end of surgery.

In addition, we will use the SpotOn zfd to log a continuous readout to provide the following data:

- a) IPH at any time during surgery and at the end of surgery/arrival in the recovery room
- b) Area under the curve for total hypothermia time during surgery
- c) Weighted hypothermia time (i.e. time spent at 35.5°C is more significant than time spent at 35.9°C)

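### The final follow-up may be completed up to 13 days before the 90-day deep SSI period closes, with no later check required, so late infections may be missed and then counted as no event

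*Protocol*

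**What the plan says.** The outcome table in Protocol section 4 gives the main-trial outcome as "definitive deep surgical site infection (SSI) within 90 days of surgery (main trial"). Section 7.6 fixes the day count: "Infection arising within 90 days of the index surgery (where day 1 is the procedure date").

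On timing, section 5 states "Data for all assessments will be captured either from routine clinical care records or by telephone contact", and the same sentence attaches the time points: "by telephone contact with participants or their GP practice at baseline, 30 (+/- 7) days and 90 (+/- 14) days". Section 7.6 repeats both windows and puts record review and the call in the same assessment: "Follow-up assessments will be undertaken by a member of the local study team through a) medical records and b) direct contact, usually by telephone". The Appendix A form has a tick box for the same 90-day window. GP and routine surveillance data come in only as a fallback: "If it is not possible to make contact with the participant, the local study team will gather follow-up data from the patient's GP".

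Section 5 (Endpoint Committee) also has an event-driven rule that does not depend on the call date. "Any post-randomisation re-admission, clinic attendance or return to theatre with signs and symptoms at the site of surgery" makes the episode a potential primary endpoint, to be adjudicated blind.

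Section 7.7 closes the study: "The end of the study is defined as the date of the last follow-up telephone call to the last participant recruited". Section 10.3 analyses the proportion with deep SSI by 90 days, using logistic regression.

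**The concern.** The outcome is defined over a fixed period, but the assessment meant to close that period may be completed before it ends. A participant reached on the first permitted day is finished under the protocol with nearly two weeks of risk remaining. No section asks for a second look, and because GP and surveillance data are needed only when contact fails, a participant reached early can end up less well covered than one who could not be reached.

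The error runs one way: the early half of the window can lose events and cannot add any. A logistic model for a 90-day proportion has no censoring, so an unrecorded infection is scored as no infection. The secondary time-to-event analysis in section 10.3 could censor at the last assessment, but the primary one cannot.

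This matters even in a pilot. The observed 90-day event rate is part of the primary endpoint (sections 1 and 5), it informs changes to the main study (section 10.1), and the pilot data will enter the main trial's final analysis (section 3). If the follow-up procedure is carried over unchanged, the gap goes with it.

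**Working it through.** **Inputs from the Protocol.** Final window 90 ± 14 days after surgery (sections 5, 7.6, Appendix A). Deep SSI through day 90 with day 1 as the procedure date (section 7.6). Deep SSI risk about 2.5%, absolute reduction 1%, power 90%, significance 5%, total about 8630 (section 3). Allocation 1:1 (section 7.4). At least 100 participants at each of three centres (section 7.1).

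**Step 1: the plan's own figure.** With p₁ = 0.025, p₂ = 0.015, Δ = 0.01 and a two-sided 5% test (sidedness is not stated with the calculation):

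- n = [1.96·√(2p̄(1−p̄)) + 1.2816·√(p₁(1−p₁) + p₂(1−p₂))]² / Δ² = 4117 per arm, 8234 in total.
- With continuity correction, n′ = (n/4)·[1 + √(1 + 4/(nΔ))]² = (4117/4)·(1 + √1.0972)² = 4315 per arm, **8630 in total**. This matches exactly, so the corrected formula is used below.

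**Step 2: the gap.** The earliest permitted assessment is 90 − 14 = 76 days after surgery. With the procedure date as day 1, that is endpoint day 77. Days 78 to 90 remain: 13 days, and 13/90 = 14.4%. If the follow-up days are themselves counted with surgery as day 1, the gap is days 77 to 90: 14 days, and 14/90 = 15.6%.

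**Step 3: average loss over the window.** Assume call days spread evenly over the 29 permitted days, a constant infection rate over the 90 days, and no late event found from records.

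- 13-day count: (13 + 12 + … + 1)/29 = 91/29 = 3.14 days, and 3.14/90 = 3.5% of events. 13/29 = 45% of participants are closed early.
- 14-day count: (14 + 13 + … + 1)/29 = 105/29 = 3.62 days, and 3.62/90 = 4.0%. 14/29 = 48% are closed early.

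**Step 4: effect on rates, power and sample size.** Multiply both event rates by (1 − share lost), the same in each arm, and reuse the Step 1 formula.

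| Scenario | Share lost | Observed rates | Power at 8630 | N for 90% power |
|---|---|---|---|---|
| No loss | 0 | 2.50% v 1.50% | 90.0% | 8630 |
| Even spread, 13-day count | 3.5% | 2.41% v 1.45% | 88.9% | 8948 |
| Even spread, 14-day count | 4.0% | 2.40% v 1.44% | 88.7% | 8998 |
| All on earliest day, 13-day count | 14.4% | 2.14% v 1.28% | 84.7% | 10116 |
| All on earliest day, 14-day count | 15.6% | 2.11% v 1.27% | 84.2% | 10252 |

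**Step 5: the pilot itself.** With 300 participants (three centres at the minimum) and a 2.5% rate, 300 × 0.025 = 7.5 events are expected. A 3.5% loss is 0.26 of an event; a 14.4% loss is 1.1 events.

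**The case against.** The strongest reply is that the call is not the only route to an event. Section 5 names routine clinical records alongside the telephone, and its endpoint rule covers any re-admission, clinic attendance or return to theatre with signs at the site, whatever the call date. Section 3 says deep infections almost always lead to repeat surgery, so most leave a hospital record. This stands, and it rules out the stronger reading that every deep infection after an early call is counted as no event. What remains is that the endpoint rule says what is sent for adjudication; it schedules no search after the last assessment. An infection treated at another hospital may not come to the local team's notice.

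The loss in the pilot is also small against the sampling error of an estimate based on some 7.5 events. That is correct for the pilot alone, but the proportion lost does not shrink as numbers grow.

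Three further inferences are tempting but not supported:

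- **Bias between arms.** Local teams are unblinded and arrange the calls, so differential timing is possible. The window is the same for both arms, and nothing in the Protocol shows that timing or late capture would differ.
- **The same gap at 30 days.** The early edge of that window precedes the end of the superficial SSI period, but Appendix A asks about events since the last contact, so the 90-day assessment covers the remaining days. That leaves a question of recall, not unobserved time.
- **The end-of-study definition as a large problem.** It can precede day 90 only for participants at the very end of recruitment. It needs aligning and adds little to the size of the loss.

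**Conclusion.** The point holds in limited form. A compliant final assessment can close a participant up to 13 days (14.4% of the risk period) before the deep SSI period ends, and no later check is required. Late infections may be missed, and are then scored as no event, unless hospital records bring them to the local team's notice.

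The likely size is modest: about 3.5 to 4% of events if calls are spread evenly, and about 14 to 16% only if every call is made on the earliest day. Both figures assume a constant infection rate and no late capture from records. The loss is smaller if infections cluster early or records catch them; the Protocol gives no data on either, or on actual call dates. The direction is certain: the 90-day event rate can only be understated. It is worth correcting because the remedy is cheap and the rate feeds the main trial.

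**What to change.** Choose one of two changes in sections 5 and 7.6, carrying the first into the Appendix A form as well:

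1. Open the final window no earlier than day 90, still closing at day 104, for both the call and the record review; or
2. Keep the present window and require a check of medical records, with GP or surveillance data, through day 90 for everyone assessed earlier.

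Under either option, make that check once for participants already assessed early. In section 7.7, do not end the study before the last participant's day-90 check. Leave the 30-day window unchanged: narrowing it would not recover unobserved time and could put at risk the section 3 progression target of Day 30 endpoint data for more than 90% of participants.

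Cost: option 1 narrows the call window from 29 to 15 days and may slightly lower on-time completion. Option 2 adds a short record check for early-contacted participants, which takes some local staff time. Neither adds a visit, and with full ascertainment through day 90 the 8630 calculation needs no adjustment on this account.

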The biggest barrier to a successful funding application for this trial is the number of participants required. Hemiarthroplasty carries a risk of deep SSI of around 2.5%. To provide 90% power to demonstrate an absolute risk reduction of 1%, using a 5% significance level, a trial will need to recruit approximately 8630 participants over a 3-year period. To ensure a robust application, we will conduct a pilot study across a limited number of NHS sites to demonstrate that the recruitment strategy, randomisation process and follow-up assessments are appropriate and effective. Provided that no major strategic changes are required, we anticipate that refinements can be adopted and the study rolled out to additional centres without a prolonged break in recruitment at pilot centres. Pilot data will subsequently be transferred to the full trial and will contribute to the final analysis.

The United Kingdom Clinical Infection Research Group (UKCIRG) is a research collaboration consisting of 43 NHS trusts in the UK. Its current interventional trials include The OVIVA Study (Oral vs. Intravenous Antibiotics in bone and joint infection) which recruits at 27 centres, and the ARREST Trial (Adjunctive Rifampicin to Reduce Early mortality in Staph aureus bacteraemia) which recruits at 30 centres. The WHITE cohort is a collaboration of 16 NHS trusts recruiting patients under a single comprehensive treatment pathway, based upon the NICE Hip Fracture Guidelines, and provides core outcome measurements collected within the framework of the UK National Hip Fracture Database. Assuming that 30 of the centres from these networks are willing to participate, progression from pilot to a definitive trial will be considered if recruitment at each pilot centre exceeds an average of 2 participants per week or projects to over 100 per year after six months of activity. A second progression target designed to assess data management strategy will be defined by follow-up data for primary endpoints at Day 30 being available for >90% of participants six months after the start of the pilot study.

4. **OBJECTIVES AND OUTCOME MEASURES**

[figure not shown]
- **Primary Objective** The primary objective of the RIIiO pilot study is to inform and assess the recruitment and data management strategies for a full trial.
- **Secondary Objectives** The secondary objective of the pilot study is to confirm the methodology for health economic evaluation in the context of the full trial.

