7.4. Randomisation and limitation of bias

Prior to surgery, participants will be randomised 1:1 in randomly permuted blocks through an established software package to either Forced Air Warming or direct contact Resistive Fabric Warming. No stratification factors will be employed. In case of software failure, randomisation envelopes will be prepared in advance under the supervision of a qualified statistician and held by the local study team for immediate use in the emergency setting.

This will be an open label trial. Although participants will not be directly informed of their randomised allocation, they may become aware of this either immediately before or upon recovery from anaesthesia. Similarly, it is not possible to blind the direct medical care team or the local study team as to which warming technology is utilised during surgery. Any consequent risk of bias will be limited by the use of a blinded end point committee for the assessment of relevant potential endpoints. For all potential deep SSIs, the end point committee will be provided with a summary of the participant's medical records relevant to the clinical episode, (including presentation, operative findings, laboratory results, radiology reports and treatment) redacted for personal identifiers and any information relating to their randomisation or intraoperative thermoregulation. At the time of randomisation, the participant's initials, NHS number and a computer-generated study number will be recorded on an enrolment log. Justification for use of NHS numbers comes from previous multicentre studies in which the randomisation software requires all

participants to have a primary identifier of the same alphanumeric structure and with no opportunity for duplicates.

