- b. Involves only skin or subcutaneous tissue related to the incision AND
- c. At least one of the following
 - i. Purulent drainage from the superficial incision
 - ii. Organisms identified from an aseptically-obtained specimen from the superficial incision or subcutaneous tissue by a culture or non-culture based microbiologic testing method which is performed for purposes of clinical diagnosis or treatment (e.g., not Active Surveillance Culture/Testing (ASC/AST).
 - Superficial incision that is deliberately opened by a surgeon, physician or other designee and culture or non-culture based testing is not performed AND
 the patient has at least one of the following signs or symptoms: pain or tenderness, localized swelling, erythema, heat
 - iv. Diagnosis of a superficial incisional SSI by a surgeon or physician.

The above definitions are adapted from the CDC surgical site infection criteria published January 2016. If required for clarification or consensus, investigators and the EPC will be referred back to the source document.

Serious adverse events (SAEs), including death (i.e. all-cause mortality), will be recorded.

Discontinuation/Withdrawal of Participants from Study

Once a participant has been randomised, they will ordinarily be included in the intention to treat (ITT) analysis. However, the Principal Investigator at each site will withdraw any randomised participant from the study if they do not subsequently undergo surgery. Each participant or their consultee has the right to withdraw from the study at any time with no obligation to give a reason for withdrawing. The participant will be asked whether or not they will allow passive follow up using routinely available NHS data. All data collected up until the point of withdrawal of consent will be included in the final analysis unless requested otherwise by the participant.

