Have you had any further surgery on your affected hip since you were last contacted by the $R//iO$ Study Team?	
If yes, what was the date(s) of the surgery?	
Details of the operation:	
Participant's Comments:	
	/

Form Completed by:

Print Name

Signature

RIIIO Pilot Study Participant Follow-Up EQ-5D-5L Questionnaire v2.0 (20th January 2017)

		-	-		
Cito :	6 m.	incode	da	ما أنصا	- 1
[Site :	ю.	ILISHI	OB	24112	61

RIIiO Pilot Study

Prescription(s)		
Have you taken antibiotics for your wound since you were last contacted by the RHiO Study Team?	Yes	No
If yes, what was the date(s) of the prescription(s)?		
Participant's Comments:		
Readmission(s)		
Have you been readmitted to any hospital since you were last contacted by the $RHiO$ Study Team?	Yes	No
If yes, what was the date(s) of admission(s)?		
Participant's Comments:		

RIIIO Pilot Study Participant Follow-Up EQ-5D-5L Questionnaire v2.0 (20th January 2017)

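### Blinded adjudication protects the primary endpoint only partly: staff who know the allocation choose which cases reach the committee, under a referral trigger narrower than the endpoint itself

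*Protocol*

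**What the plan says.** Three parts of the protocol govern how a deep SSI reaches the blinded committee.

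- **Section 5, Endpoint Committee.** The trigger is "Any post-randomisation re-admission, clinic attendance or return to theatre with signs and symptoms at the site of surgery". A parenthesis glosses these events as possible deep SSIs. The same subsection adds: "Secondary endpoints, including SAEs and data for resource utilisation, will be determined directly by the local investigators". Superficial SSI is a secondary endpoint.
- **Section 5 (opening text) and Section 7.4.** Both use broader wording. Wherever a potential deep SSI is identified, a redacted summary goes to the committee, and no setting is named.
- **Section 7.6.** Deep SSI is counted for 90 days with the procedure date as day 1. It can be met by purulent deep drainage, by a deep incision that dehisces or is opened, aspirated or biopsied, or by evidence on examination or imaging. Superficial SSI can rest on "Diagnosis of a superficial incisional SSI by a surgeon or physician" alone.

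Section 7.4 concedes that "it is not possible to blind the direct medical care team or the local study team" and relies on the committee to limit the resulting bias. Section 7.6 gives follow-up to that same local team. The Appendix A telephone form asks about wound concerns, further hip surgery, readmission and "Have you taken antibiotics for your wound". No rule says that a positive answer goes to the committee. Section 7.6 says only that further clinical review is requested where necessary.

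**The concern.** A blinded committee can reject a referred case that is not a deep infection. It cannot recover a deep infection that was never sent. Its protection is therefore limited by the referral step, and here that step is taken by people who know the arm, with no blinded or central screen for candidates described.

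Two features of the Endpoint Committee wording widen the gap. The gloss invites staff to decide first whether a case is possibly deep, so the line between deep and superficial, which defines the primary endpoint, can be drawn before blinding applies. The list of settings also leaves out an infection managed on the ward during the index stay without return to theatre, and one managed only in the community, although either could meet the Section 7.6 definition.

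Two consequences are possible and should be kept apart. Cases lost equally in both arms lower the observed event rate, which the pilot is meant to estimate, and reduce power. Cases lost unequally bias the comparison.

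**Working it through.** **1. The wordings side by side**

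| Place | What is referred or counted | Setting |
|---|---|---|
| Section 5, Endpoint Committee | Events with local signs and symptoms, glossed as possible deep SSI | Re-admission, clinic, return to theatre |
| Section 5 opening text; Section 7.4 | Any potential deep SSI | None named |
| Section 7.6 definition | Deep SSI, procedure date as day 1, to 90 days | Any |

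The first row is narrower than the other two. An index-stay return to theatre is covered, since the trigger is post-randomisation and not post-discharge.

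**2. Reproducing the planned size of the full trial**

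Section 3 gives the inputs: "Hemiarthroplasty carries a risk of deep SSI of around 2.5" per cent, and "To provide 90% power to demonstrate an absolute risk reduction of 1%, using a 5% significance level". The arms are therefore 2.5% and 1.5%. Section 10.3 tests for superiority of either arm (two-sided) and Section 7.4 allocates 1:1.

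- Uncorrected: n = [1.960·√(2·0.02·0.98) + 1.2816·√(0.025·0.975 + 0.015·0.985)]² / 0.01² = (0.3881 + 0.2536)² / 0.0001 ≈ 4117 per arm.
- With continuity correction: (n/4)·[1 + √(1 + 4/(n·0.01))]² ≈ 4315 per arm, or 8630 in total.

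This matches the protocol exactly: "a trial will need to recruit approximately 8630 participants over a 3-year period". The sample size is not in dispute. It sets the scale for what follows.

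**3. Equal loss in both arms** (the loss fractions are assumptions; the protocol gives none)

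Power = Φ[(d − 1.960·SE₀)/SE₁] with 4315 per arm, without continuity correction.

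| Loss | Observed rates | Calculation | Power |
|---|---|---|---|
| 0% | 2.50% v 1.50% | (0.0100 − 1.960·0.003014)/0.003012 = 1.36 | 91.3% |
| 10% | 2.25% v 1.35% | (0.0090 − 1.960·0.002862)/0.002861 = 1.19 | 88.2% |
| 20% | 2.00% v 1.20% | (0.0080 − 1.960·0.002701)/0.002700 = 1.00 | 84.2% |

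The starting value is above 90% because 8630 includes the continuity correction and this formula does not. Loss that is independent of arm does not inflate type I error.

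**4. Unequal referral, no true difference** (true rate 2.5% in both arms; the referral fractions are again assumptions)

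Rejection probability with 4315 per arm. For 100% v 90% referral the observed rates are 2.50% and 2.25%, the spurious difference is 0.25 percentage points (a quarter of the 1-point target) and the SE is 0.00328. The ratio is 0.0025/0.00328 = 0.763, so the rejection probability is Φ(0.763 − 1.960) + Φ(−0.763 − 1.960) = 0.1156 + 0.0032 ≈ 11.9%.

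| Referral by arm | Type I error at 8630 |
|---|---|
| 100% v 95% | 6.6% |
| 100% v 90% | 11.9% |
| 100% v 80% | 34.7% |

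**5. The same at pilot size**

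Three sites with a minimum of 100 each (Section 7.1) give 300, or 150 per arm. Expected deep SSIs are 150 × 0.025 = 3.75 per arm, so losing 10% in one arm costs about 0.4 of an event. The same formula gives about 5.2% for 100% v 90% and about 6.0% for 100% v 80%. The normal approximation is rough with so few events, but the inflation is clearly slight.

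**The case against.** The strongest case against has four parts.

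- **The broad wording already covers every setting.** Section 5's opening text and Section 7.4 refer any potential deep SSI. Follow-up asks about the wound and possible infection, uses GP and surveillance data if contact fails, and can lead to clinical review. This stands in part. A reader might infer that index-stay and community infections are excluded outright, and the documents do not support that. What remains is two unreconciled triggers, with the passage that defines a potential primary endpoint being the narrower.
- **Few deep infections would be missed by setting.** Section 3 says deep infections almost always need repeat surgery, and return to theatre is on the list. Wound antibiotics alone do not meet the deep definition. This stands, and the setting gap is probably small. It does not settle the depth boundary, because the statement concerns infections already classified as deep.
- **The trigger is event-based.** Read without its gloss, it sends symptomatic attendances whatever the local label. A reader might infer that a case labelled superficial is never adjudicated. That goes too far: such a case need not be adjudicated, because the gloss allows staff to hold it back.
- **The error rates belong to a future trial and rest on assumed differentials.** This is correct. The pilot concerns recruitment and data management, a formal efficacy analysis is foreseen only above 1000 participants, and the full-trial analysis is pending pilot recommendations. However, Section 3 carries pilot data into the final analysis, so endpoints collected under this rule stay in the dataset.

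**Conclusion.** The point holds in a limited form. Blinded adjudication protects the primary endpoint in part: classification of referred cases is blinded, but selection for referral is not, and the trigger in the Endpoint Committee subsection is narrower than both the other referral wording and the endpoint definition.

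A reader might go further and conclude that the committee gives no protection. The documents do not support that. Blinded classification is a real safeguard, many trigger events are recorded facts, and Section 7.4 claims only that bias is limited.

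The size depends on referral fractions that the protocol does not give. Equal loss of an assumed 10-20% would understate the event rate (2.5% seen as 2.25-2.0%) and reduce power at 8630 from about 91% to 88-84%. Bias arises only if referral differs by arm. Nothing in the documents shows that it will, and the investigators declare equipoise in Section 14.7. If it were 100% against 90%, type I error at 8630 would be about 12%; at about 300 participants it would hardly move. The change should be made, because it is cheap and because pilot endpoints are carried forward.

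**What to change.** Reconcile the two referral wordings in Section 5 and the one in Section 7.4 into a single rule that covers any setting from the day of surgery, and delete the gloss about possible deep SSI. Trigger referral by recorded facts, whatever depth the local team assigns:

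- any re-operation on or aspiration of the hip;
- any positive wound, deep or joint sample;
- any imaging evidence of infection;
- any locally recorded SSI, including superficial;
- any antibiotic for the wound, recorded in the notes or reported in Appendix A.

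Send redacted summaries of all of these to the existing committee, which decides deep SSI yes or no. The wound-antibiotic item is a screen and not a criterion for the endpoint. A locally recorded SSI still involves local judgement, which is why it should be one trigger among several and not the only one. Central adjudication of superficial SSI as an endpoint in its own right is optional.

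**Cost.** Wording changes in Sections 5 and 7.4 and matching CRF fields. The committee will review more short summaries, in a number that the documents do not allow to be estimated precisely, since they give no frequency for wound antibiotics, positive samples or non-infective re-operations. No new staff or participant procedures are needed.
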